7.3. Body Weight, Height, and Vital Signs

Descriptive statistics will be provided for vital signs and body weight as follows:

- Baseline values
- Values at each postbaseline analysis window
- Change from baseline at each postbaseline analysis window

A baseline value will be defined as the last nonmissing value obtained on or prior to the date of first dose of B/F/TAF. Change from baseline to a postbaseline visit will be defined as the postbaseline value minus the baseline value.

In the case of multiple values in an analysis window, data will be selected for analysis as described in Section 3.8.3. No formal statistical testing is planned.

A by-subject listing of vital signs will be provided by subject ID number and visit in chronological order. In the same listing, a by-subject listing of body weight, height, and BMI will be provided.

7.4. Prior and Concomitant Medications

7.4.1. Antiretroviral Medications

Any nonstudy ARV medications used prior to, during, or after the study (if collected) are recorded on the ARV eCRF. All ARV medications recorded on the ARV eCRF will be coded using the Gilead-modified World Health Organization (WHO) Drug Dictionary for ARV medication. The WHO preferred name and drug code will be attached to the clinical database. All ARV medications recorded on the ARV eCRF will be listed. No inferential statistics will be provided.

7.4.2. Concomitant Non-Antiretroviral Medications

Concomitant non-ARV medications (ie, medications other than study drug that are taken while receiving study drug) will be coded using the WHO Drug Dictionary. The WHO preferred drug name and drug code will be attached to the clinical database. Use of concomitant medications from the first dose date to the last dose date of B/F/TAF will be summarized (number and percentage of subjects) by preferred drug name. Multiple drug use (by preferred drug name) will be counted only once per subject. The summary will be sorted by decreasing order of total frequency.

If the start or stop date of non-ARV medications is incomplete, the month and year (or year alone, if month is not recorded) of the start or stop date will be used to determine whether the non-ARVs are concomitant. The medication is concomitant if the month and year of the start or stop (or year of the start or stop, if month is not recorded) of the medication does not meet either of the following criteria:

- The month and year of start of the medication is after the last dose date of B/F/TAF
- The month and year of stop of the medication is before the first dose date of B/F/TAF

If the start and stop date of non-ARV medications are complete, the start date is not after the last dose date and the stop date is not before the first dose date, or the non-ARV medications are marked as ongoing and start date is on or before the last dose date, the non-ARV medications are concomitant.

Summaries of non-ARV concomitant medications will be provided for the Safety Analysis Set. Subjects with any non-ARV concomitant medications will be listed. No inferential statistics will be provided.

Additionally, for each subject, the number of unique chronic medications (based on preferred drug name) that the subject was receiving at baseline (ie, on the date of the first dose of study drug) will be calculated. Chronic medications are defined as those (1) given orally, and (2) given for a duration of at least 30 days. Number of chronic medications at baseline will be summarized using descriptive statistics. Additionally, chronic medications will be summarized by medication class using ATC Level 1 and ATC Level 2, separately.

7.5. Electrocardiogram Results

A shift table of the investigators' assessment of ECG results at Week 48 and Week 96 compared with baseline values will be presented using the following categories: normal; abnormal, not clinically significant; abnormal, clinically significant; or missing. The number and percentage of subjects in each cross-classification group of the shift table will be presented. Subjects with a missing value at baseline or postbaseline will not be included in the denominator for percentage calculation.

A by-subject listing for ECG assessment results will be provided by subject ID number and visits in chronological order.

7.6. Other Safety Measures

A data listing will be provided for subjects experiencing pregnancy during the study. Physical examination was not collected in the eCRF. Therefore, it will not be included in the analysis.

7.7. Subgroup Analyses for Safety Endpoints

No subgroup analyses are planned for the Week 96 analysis.

7.8. Changes From Protocol-Specified Safety Analyses

No change from protocol-specified safety analysis is planned.

8. PHARMACOKINETIC ANALYSES

There are no PK analyses planned.

9. PATIENT REPORTED OUTCOMES

The patient-reported outcomes (PROs) include the following assessments:

- Visual Analog Scale (VAS) Adherence Questionnaire (assessed at Day 1, Weeks 4, 12, 24, 36, 48, 60, 72, 84, 96)

Summaries will use the safety analysis set. Assessments will be listed using the all enrolled analysis set. Summaries will include data up to 30 days after permanent discontinuation of B/F/TAF study drug.

9.1. Medication Adherence Questionnaire

Adherence will be assessed by the medication adherence questionnaire that includes a VAS and 2 additional questions.

For the VAS, the subject is asked to describe their adherence to their ARV regimen by using a linear scale (0% – 100%) to indicate what percent of medications was taken in the last 30 days (0% = taken none of prescribed anti-HIV medication, and 100% = taken all doses of prescribed anti-HIV medication). The 2 additional questions ask how many days the subject has missed medications in the last 30 days and how many days the subject has missed medications in the last 4 days.

9.1.1. VAS Statistical Analysis Method

The VAS (%) absolute value at each study visit will be summarized using descriptive statistics.

Number of days with missed doses in the past 30 days and past 4 days will be summarized categorically (< 2, 2 to < 4, 4 to < 6, \geq 6 for the past 30 days; 0 and $>$ 0 for the past 4 days) for each study visit.

11. SOFTWARE

SAS® Version 9.4 (SAS Institute Inc., Cary, NC, USA) is to be used for all programming of tables, listings, and figures.

12. SAP REVISION

Revision Date (dd month, yyyy)	Section	Summary of Revision	Reason for Revision

Appendix 1. Study Procedures Table

Study Procedure	Screening ^a	Day 1 ^b	End of Week ^c									Early Study Drug Discontinuation (ESDD) ^d	30-Day Follow-up
			4	12	24	36	48	60	72	84	96		
Informed Consent	X												
Medical History	X												
Concomitant Medications	X	X	X	X	X	X	X	X	X	X	X	X	X
Adverse Events	X	X	X	X	X	X	X	X	X	X	X	X	X
Complete Physical Exam ^e	X	X					X				X		
Symptom Directed Physical Exam			X	X	X	X			X	X	X		X
Vital Signs and Weight	X	X	X	X	X	X	X	X	X	X	X	X	X
Height	X												
12 lead ECG	X						X				X		X
Urinalysis and Urine Chemistry	X	X	X	X	X	X	X	X	X	X	X	X	X ^p
Renal Safety Evaluations Urine ^f		X	X	X	X		X	X	X	X	X		
Biomarkers: inflammation, platelet, renal ^g		X	X	X	X		X	X	X	X	X		
Urine Storage Sample		X	X	X	X	X	X	X	X	X	X	X	
Chemistry Profile ^h	X	X	X	X	X	X	X	X	X	X	X	X	X
Hematology Profile ⁱ	X	X	X	X	X	X	X	X	X	X	X	X	X
CD4+ Cell Count	X	X	X	X	X	X	X	X	X	X	X	X	
Plasma HIV 1 RNA ^j	X	X	X	X	X	X	X	X	X	X	X	X	
HBV and HCV Serologies ^k	X												
Cystatin C		X											
Estimated GFR ^l	X	X	X	X	X	X	X	X	X	X	X	X	

CCI

Study Procedure	Screening ^a	Day 1 ^b	End of Week ^c									Early Study Drug Discontinuation (ESDD) ^d	30-Day Follow-up
			4	12	24	36	48	60	72	84	96		
Whole Blood Sample ^m	X	X											
Metabolic Assessments ⁿ		X			X		X				X		
Plasma Storage Sample ^o		X	X	X	X	X	X	X	X	X	X	X	
Patient reported outcomes: VAS		X	X	X	X	X	X	X	X	X	X	X	
Patient reported outcome: HIVTSQs		X											
Patient reported outcome: HIVTSQ ^c			X		X		X					X	
Patient reported outcome: EQ 5D		X			X		X						
Patient reported outcome: SF 36		X			X		X						
Patient reported outcome: FACIT F		X			X		X						
HIV 1 Genotype/Phenotype ^q							X		X		X	X	
Study Drug Dispensation and Accountability		X	X	X	X	X	X	X	X	X	X	X ^r	

a Evaluations to be completed within 30 days prior to Day 1 visit.

b Subjects will be dispensed study drug at the Day 1 visit; initiation of treatment with the study drug must take place within 24 hours after the Day 1 visit.

c All study visits are to be scheduled relative to the Day 1 visit date. Visit windows are \pm 2 days of the protocol specified date through Week 12, \pm 6 days of the protocol specified date through Week 96. The Week 24, 48 and 96 visits window is \pm 6 weeks of the visit date, if notified by Gilead. Unless notified by Gilead, the Week 24, 48 and 96 visits should be completed within \pm 6 days of the visit date. For the purpose of scheduling a 30 Day Follow Up Visit, a \pm 6 days window may be used. Those subjects who prematurely discontinue study drug and continue in the study through at least one subsequent visit after the Early Study Drug Discontinuation Visit will not be required to complete the 30 Day Follow Up Visit.

d Early Study Drug Discontinuation visit to occur within 72 hours of last dose of study drug. Subjects will be asked to continue attending the scheduled study visits through the Week 96 visit even as the subject discontinues study drug.

e Complete physical examination (urogenital/anorectal exams will be performed at the discretion of the investigator).

[figure not shown]
f Urine for renal safety, including retinol binding protein, and beta 2 microglobulin, will be collected. Samples for renal safety will be collected fasted. If the subject has not fasted prior to the visit, the visit may proceed, but the subject must return within 72 hours in a fasted.

CCI

- g Inflammation may include cystatin C, IL 6, hs CRP, sCD14, sCD163, sTNF 1R, and Lp PLA2; Platelet and coagulation function may include soluble glycoprotein VI (sGPVI), P selectin, soluble CD40 ligand, and D dimer will be collected. Urine for renal safety, including retinol binding protein, and beta 2 microglobulin, will be collected. Samples for renal safety will be collected fasted. If the subject has not fasted prior to the visit, the visit may proceed, but the subject must return within 72 hours in a fasted state. A portion of the biomarker blood sample obtained at Day 1, Weeks 4, 12, 24, 48, 60, 72, 84 and 96 may be utilized to assess study drug PK. This will be a random sample with the date and time of the subject's last medication dose recorded.
- h Chemistry profile: alkaline phosphatase, AST, ALT, total bilirubin, direct and indirect bilirubin, total protein, albumin, bicarbonate, BUN, calcium, chloride, creatinine, glucose, potassium, and sodium. At Day 1, Weeks 24, 48 and 96 analyses of glucose will be done as part of the fasting metabolic assessments and not as part of the chemistry profile.
- i CBC with differential and platelet count.
- j For the management of virologic rebound please refer to Protocol Section 6.12.
- k Hepatitis B virus surface antigen (HBsAg), Hepatitis B virus surface antibody (HBsAb) and Hepatitis B virus core antibody (HBcAb).
- l Estimated GFR according to the Cockcroft Gault formula for creatinine clearance.
- m Whole blood sample for virology analysis.
- n Metabolic Assessments: Fasting glucose and lipid panel (total cholesterol, HDL, direct LDL, triglycerides). If the subject has not fasted prior to the visit, the visit may proceed, but the subject must return within 72 hours in a fasted state.
- o Plasma storage sample for safety and/or virology (Day 1, Weeks 4-96, and ESDD).
- p Urinalysis only.
- q The geno/pheno is only done if the last HIV 1 RNA is > 200 copies/mL.
- r Drug accountability only; study drug will not be dispensed at this visit.

Appendix 2. Flowchart of US FDA-defined Snapshot Algorithm (for Switch Trial)

The following flowchart for US FDA-defined snapshot algorithm is based on the US FDA Guidance on Human Immunodeficiency Virus-1 Infection: Developing Antiretroviral Drugs for treatment {U. S. Department of Health and Human Services 2015}.

* On-Treatment HIV-1 RNA data include all HIV-1 RNA data for subjects who are on-going and HIV-1 RNA data up to 1 day after the last dose date of study drug for subjects who prematurely discontinue or complete study drug.

Appendix 3. Cardiovascular or Cerebrovascular Events

An adverse event record will be flagged as a cardiovascular or cerebrovascular event if its MedDRA PT is included in the pre-specified PT list, which includes all PTs from the narrow search of the following 3 SMQs under MedDRA v23.0 provided by Gilead PVE (search name: Ischemic cardiac and cerebral events narrow) and reviewed by Gilead medical monitors.

	SMQ Source
Cardiovascular or Cerebrovascular Events	Ischaemic central nervous system vascular conditions (SMQ) – Narrow Scope Term
	Myocardial infarction (SMQ) - Narrow Scope Term
	Other ischaemic heart disease (SMQ) - Narrow Scope Term

Appendix 4. Hepatic Events

An adverse event record will be flagged as a hepatic event if its MedDRA PT is included in this pre-specified PT list, which includes all PTs from the broad search of the following 15 SMQs under MedDRA v23.0 provided by Gilead PVE (search name: Non-infectious, non-congenital hepatobiliary disorders) and reviewed by Gilead medical monitors.

	SMQ Source
Hepatic Events (HEP)	Biliary neoplasms benign (incl cysts and polyps) (SMQ)
	Biliary malignant tumours (SMQ)
	Biliary tumours of unspecified malignancy (SMQ)
	Biliary system related investigations, signs and symptoms (SMQ)
	Biliary tract disorders (SMQ)
	Gallbladder related disorders (SMQ)
	Gallstone related disorders (SMQ)
	Cholestasis and jaundice of hepatic origin (SMQ)
	Hepatic failure, fibrosis and cirrhosis and other liver damage-related conditions (SMQ)
	Hepatitis, non-infectious (SMQ)
	Liver neoplasms, benign (incl cysts and polyps) (SMQ)
	Liver malignant tumours (SMQ)
	Liver tumours of unspecified malignancy (SMQ)
	Liver related investigations, signs and symptoms (SMQ)
	Liver-related coagulation and bleeding disturbances (SMQ)

Appendix 5. Medical History

Number and percentage of subjects with selected medical history of Diabetes Mellitus, Hypertension, Cardiovascular Disease, and Hyperlipidemia will be summarized by treatment as baseline disease characteristics. A subject who had medical history of one of these diseases is a subject who experience at least one of the following events:

- At least 1 medical history record with MedDRA PT (mh.MDRPT) in the selected PT listing for the corresponding disease with start date on or prior to the first dose date.
- At least 1 adverse event record with MedDRA PT (ae.MDRPT) in the selected PT listing for the corresponding disease with start date on or prior to the first dose date.
- At least 1 concomitant medications record with medication class and indication in the following selected listing for the corresponding disease with start date on or prior to the first dose date.

If the start date is incomplete but the month and year (or year alone) of the start date is the same as or before the month and year (or year alone) of the first dosing date of study drug, then the event will be included. If the start date is completely missing, the event will be included.

Four variables (ie, DIABETES, HTENSION, CARDDIS, and HLIPDEM) will be added to raw Medical History and Adverse Events datasets. A medical history or an adverse event record will be flagged for a disease of interest if its MedDRA PT included in the pre-specified PT list for the corresponding disease of interest, which include all PTs from the narrow or broad search of the following SMQs under MedDRA 23.0 provided by Gilead DSPH and reviewed by Gilead medical monitors.

Disease of Interest	SMQ Source
Diabetes Mellitus (DIABETES)	Hyperglycaemia/new onset diabetes mellitus (SMQ) Narrow Scope Term
Hyperlipidemia (HLIPDEM)	Dyslipidaemia (SMQ)
Hypertension (HTENSION)	Hypertension (SMQ)
Cardiovascular disease (CARDDIS)	Ischaemic central nervous system vascular conditions (SMQ) Narrow Scope Term
	Myocardial infarction (SMQ) Narrow Scope Term
	Other ischaemic heart disease (SMQ) Narrow Scope Term

Similarly, four variables (ie, DIABETES, HTENSION, CARDDIS, and LIPMOD) will be added to raw Concomitant Medication dataset. A concomitant medication record will be flagged for a disease of interest if its medication preferred term and indication included in the following listing for the corresponding disease of interest.

The selected combination of medication preferred term and indication are listed as follows, which was reviewed by Gilead medical monitors.

	Indication (CMINDC)	Preferred Term
Hypertension (HTENSION)		
1	HYPERTENSION	ACETYLSALICYLATE LYSINE
2	HYPERTENSION	ACETYLSALICYLIC ACID
3	ARTERIAL HYPERTENSION	ALFUZOSIN
4	ARTERIAL HYPERTENSION	AMLODIPINE
5	HIGH BLOOD PRESSURE	AMLODIPINE
6	HYPERTENSION	AMLODIPINE
7	HYPERTENSION	AMLODIPINE BESILATE
8	HYPERTENSION	AMLODIPINE BESILATE;INDAPAMIDE;PERINDOPRIL ARGININE
9	ARTERIAL HYPERTENSION	AMLODIPINE BESILATE;PERINDOPRIL ARGININE
10	HIGH BLOOD PRESSURE	AMLODIPINE BESILATE;PERINDOPRIL ARGININE
11	HYPERTENSION	AMLODIPINE;PERINDOPRIL ARGININE
12	HYPERTENSION	BARNIDIPINE HYDROCHLORIDE
13	ARTERIAL HYPERTENSION	BISOPROLOL
14	HYPERTENSION	BISOPROLOL
15	HIGH BLOOD PRESSURE	BISOPROLOL FUMARATE
16	HYPERTENSION	BISOPROLOL FUMARATE
17	ARTERIAL HYPERTENSION	BISOPROLOL FUMARATE;HYDROCHLOROTHIAZIDE
18	HIGH BLOOD PRESSURE	CANDESARTAN
19	HYPERTENSION	CANDESARTAN
20	HYPERTENSION	CELIPROLOL HYDROCHLORIDE
21	HYPERTENSION	DOXAZOSIN MESILATE
22	ARTERIAL HYPERTENSION	EDOXABAN TOSILATE
23	ARTERIAL HYPERTENSION	ENALAPRIL
24	HIPERTENSION	ENALAPRIL
25	ARTERIAL HYPERTENSION	ENALAPRIL MALEATE;HYDROCHLOROTHIAZIDE
26	ARTERIAL HYPERTENSION	HYDRALAZINE HYDROCHLORIDE
27	ARTERIAL HYPERTENSION	HYDROCHLOROTHIAZIDE
28	HYPERTENSION	HYDROCHLOROTHIAZIDE
29	HIGH BLOOD PRESSURE	HYDROCHLOROTHIAZIDE;IRBESARTAN
30	HYPERTENSION	HYDROCHLOROTHIAZIDE;IRBESARTAN
31	HYPERTENSION	HYDROCHLOROTHIAZIDE;OLMESARTAN
32	HYPERTENSION	HYDROCHLOROTHIAZIDE;TELMISARTAN
33	HYPERTENSION	HYDROCHLOROTHIAZIDE;ZOFENOPRIL CALCIUM

	Indication (CMINDC)	Preferred Term
34	ARTERIAL HYPERTENSION	IRBESARTAN
35	HIGH BLOOD PRESSURE	IRBESARTAN
36	HYPERTENSION	IRBESARTAN
37	SYSTEMATIC BLOOD HYPERTENSION	IRBESARTAN
38	HYPERTENSION	ISOSORBIDE MONONITRATE
39	HYPERTENSION	LERCANIDIPINE
40	ARTERIAL HYPERTENSION	LISINOPRIL
41	SYSTEMIC HYPERTENSION	LISINOPRIL
42	ARTERIAL HYPERTENSION	LOSARTAN
43	HYPERTENSION	LOSARTAN
44	HYPERTENSION	NEBIVOLOL HYDROCHLORIDE
45	HYPERTENSION	OLMESARTAN
46	ARTERIAL HYPERTENSION	OLMESARTAN MEDOXOMIL
47	HYPERTENSION	OLMESARTAN MEDOXOMIL
48	ARTERIAL HYPERTENSION	PERINDOPRIL ARGININE
49	HYPERTENSION	PERINDOPRIL ERBUMINE
50	ARTERIAL HYPERTENSION	PHENPROCOUMON
51	ARTERIAL HYPERTENSION	RAMIPRIL
52	HIGH BLOOD PRESSURE	RAMIPRIL
53	HYPERTENSION	RAMIPRIL
54	ARTERIAL HYPERTENSION	TORASEMIDE
55	HIGH BLOOD PRESSURE	URAPIDIL
56	HYPERTENSION	VERAPAMIL
57	HYPERTENSION	ZOFENOPRIL

	Indication (CMINDC)	Preferred Term
Hyperlipidemia (LIPMOD)		
1	DYSLIPEMIA	ATORVASTATIN
2	DYSLIPIDEMIA	ATORVASTATIN
3	HIPERCHOLESTEROLEMIA	ATORVASTATIN
4	HIPERCOLESTEROLEMIA	ATORVASTATIN
5	HYPERCHOLESTEROLEMIA	ATORVASTATIN
6	HYPERLIPEMIA	ATORVASTATIN
7	HYPERLIPIDAEMIA	ATORVASTATIN
8	HYPERTRIGLYCERIDEMIA	ATORVASTATIN
9	MILD HYPERCHOLESTEROLEMIA	ATORVASTATIN
10	DISLIPEMIA	ATORVASTATIN CALCIUM
11	HYPER COLESTEROLEMY	ATORVASTATIN CALCIUM
12	HYPERCHOLESTEROLEMIA	ATORVASTATIN CALCIUM
13	HYPERCHOLESTEROLEMIE	ATORVASTATIN CALCIUM
14	HYPERTRIGLYCERIDEMIA	GEMFIBROZIL
15	HYPERTRIGLYCERIDEMIA	OMEGA 3 TRIGLYCERIDES
16	DISLIPEMIA MIXTA	PITAVASTATIN
17	ELEVATED LIPIS	PRAVASTATIN
18	ESSENTIAL HYPERCHOLESTEROLEMIA	PRAVASTATIN
19	HYPERLIPEMIA	PRAVASTATIN
20	HYPERCHOLESTEROLEMIA	PRAVASTATIN SODIUM
21	DYSLIPIDEMIA	ROUVASTATIN
22	HYPERCHOLESTEROLEMIA	ROUVASTATIN
23	HIPERCOLESTEROLEMIA	ROUVASTATIN
24	SMALL FIBROUS PLATE	ROUVASTATIN
25	CARDIOVASCULAR PREVENTION	ROUVASTATIN CALCIUM
26	DYSLIPIDEMIA	ROUVASTATIN CALCIUM
27	HIPERCHOLESTERIEMIA	ROUVASTATIN CALCIUM
28	HIPERCHOLESTEROLEMIA	ROUVASTATIN CALCIUM
29	HIPERCHOLESTEROLEMY	ROUVASTATIN CALCIUM
30	HIPERCHOLESTEROLEMIA, CONTINUED ELEVATED LEVELS OF LDL	SIMVASTATIN
31	HYPERLIPEMIA	SIMVASTATIN

	Indication (CMINDC)	Preferred Term
Diabetes Mellitus (DIABETES)		
1	DIABETES MELLITUS TYPE 2	DAPAGLIFLOZIN;METFORMIN
2	MELLITUS DIABETES	EMPAGLIFLOZIN
3	DIABETES MELLITUS	GLICLAZIDE
4	DIABETES MELLITUS	INSULIN GLARGINE
5	MELLITUS DIABETES TYPE II	LINAGLIPPTIN
6	DIABETES	METFORMIN
7	DIABETES MELLITUS	METFORMIN
8	DIABETES MELLITUS TYPE 2	METFORMIN
9	HYPERGLYCEMIA	METFORMIN
10	MELLITUS DIABETES	METFORMIN
11	TYPE 2 DIABETES MELLITUS	METFORMIN
12	DIABETES	METFORMIN EMBONATE
13	DIABETES	METFORMIN HYDROCHLORIDE
14	METABOLE SYNDROME (INSULIN RESISTANCE)	METFORMIN HYDROCHLORIDE
15	MELLITUS DIABETES	METFORMIN HYDROCHLORIDE;SITAGLIPPTIN PHOSPHATE

	Indication (CMINDC)	Preferred Term
	Cardiovascular disease (CARDDIS)	
1	AORTIC VALVE DISEASE	ACENOCOUMAROL
2	ACUTE MYOCARDIAL INFARCTION	ACETYLSALICYLATE LYSINE
3	BIFEMORAL ARTERY BYPASS SURGERY	ACETYLSALICYLATE LYSINE
4	CARDIOPATHY	ACETYLSALICYLATE LYSINE
5	STROKE	ACETYLSALICYLIC ACID
6	MYOCARDIAL INFARCTION	ACETYLSALICYLIC ACID;CLOPIDOGREL BISULFATE
7	ISCHEMIA CARDIOMYOPATHY	AMILORIDE;HYDROCHLOROTHIAZIDE
8	ARYTHMIA	AMIODARONE
9	ATRIAL FIBRILLATION	AMIODARONE
10	CARDIAC RHYTHM DISORDER	AMIODARONE
11	ANGINA	AMOXICILLIN TRIHYDRATE;CLAVULANATE POTASSIUM
12	INFECTIOUS ENDOCARDITIS ON A PROSTHETIC VALVE WITHOUT MICROBIOLOGICAL AFFILIATION, CARDIOEMBOLISM, AND RECURRENT ACUTE CEREBRAL VASCULAR DISEASE.	AMPICILLIN
13	ATRIAL FIBRILLATION	ATENOLOL
14	HYPERTENSION	ATENOLOL
15	ISCHEMIC HEART DISEASE	ATENOLOL
16	ISCHEMIC STROKE IN THE TERRITORY OF LEFT MIDDLE CEREBRAL ARTERY	BEMIPARIN SODIUM
17	ARYTHMIA	BISOPROLOL FUMARATE
18	PROPHYLAXIS FOR MYOCARDIAL INFARCTION	BISOPROLOL FUMARATE
19	ISCHEMIA CARDIOMYOPATHY	CLOPIDOGREL
20	CARDIOPATHY	CLOPIDOGREL BISULFATE
21	INFECTIOUS ENDOCARDITIS ON A PROSTHETIC VALVE WITHOUT MICROBIOLOGICAL AFFILIATION, CARDIOEMBOLISM, AND RECURRENT ACUTE CEREBRAL VASCULAR DISEASE.	CLOXACILLIN
22	ATRIAL FIBRILLATION	DABIGATRAN
23	INFECTIOUS ENDOCARDITIS ON A PROSTHETIC VALVE WITHOUT MICROBIOLOGICAL AFFILIATION, CARDIOEMBOLISM, AND RECURRENT ACUTE CEREBRAL VASCULAR DISEASE.	DALBAVANCIN
24	INFECTIOUS ENDOCARDITIS ON A PROSTHETIC VALVE WITHOUT MICROBIOLOGICAL AFFILIATION, CARDIOEMBOLISM, AND RECURRENT ACUTE CEREBRAL VASCULAR DISEASE.	DAPTOMYCIN
25	MYOCARDIAL INFARCTION	DOXAZOSIN MESILATE

	Indication (CMINDC)	Preferred Term
26	ISCHEMIA CARDIOMYOPATHY	ENALAPRIL
27	ATRIAL FIBRILLATION	ENOXAPARIN SODIUM
28	ARRHYTHMIA	FLECAINIDE
29	ACUTE PULMONARY ODEMA	FUROSEMIDE
30	CARDIAC ARREST	FUROSEMIDE
31	PEDAL ODEMA	FUROSEMIDE
32	INFECTIOUS ENDOCARDITIS ON A PROSTHETIC VALVE WITHOUT MICROBIOLOGICAL AFFILIATION, CARDIOEMBOLISM, AND RECURRENT ACUTE CEREBRAL VASCULAR DISEASE.	HEPARIN
33	STROKE	HEPARIN
34	ISCHEMIC HEART DISEASE	HYDROCHLOROTHIAZIDE
35	MYOCARDIAL INFARCTION	LERCANIDIPINE
36	ISCHEMIA CARDIOMYOPATHY	OMEPRAZOLE
37	CARDIOVASCULAR PREVENTION	PRASUGREL HYDROCHLORIDE
38	ARTERIOPATHY	PRAVASTATIN
39	HEART RHYTHME DISTURBANCE	PROPAFENONE
40	CARDIOVASCULAR PREVENTION	RAMIPRIL
41	LOWER LIMB ODEMA	RAMIPRIL
42	ACUTE MYOCARDIAL INFARCTION	ROSUVASTATIN CALCIUM
43	CARDIOVASCULAR PREVENTION	ROSUVASTATIN CALCIUM
44	PROPHYLAXIS FOR MYOCARDIAL INFARCTION	ROSUVASTATIN CALCIUM
45	ATRIAL FIBRILLATION	SOTALOL HYDROCHLORIDE
46	ARYTHMIA	WARFARIN SODIUM
47	ATRIAL FIBRILLATION	WARFARIN SODIUM

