## **7.2. Investigator Requirements and Instructions for Reporting Adverse Events and Serious Adverse Events to Gilead**

Requirements for collection prior to study drug initiation:

After informed consent, but prior to initiation of study medication, the following types of events should be reported on the eCRF: all SAEs and adverse events related to protocol-mandated procedures.

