7.1.5. Treatment-Emergent Adverse Events

7.1.5.1. Definition of Treatment-Emergent Adverse Events

Treatment-emergent adverse events (TEAEs) are defined as 1 or both of the following:

- Any AEs with an onset date on or after the B/F/TAF start date and no later than 30 days after permanent discontinuation of B/F/TAF, or
- Any AEs leading to premature discontinuation of B/F/TAF.

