7.1.5.2. Incomplete Dates

If the onset date of the AE is incomplete and the AE stop date is not prior to the first dosing date of B/F/TAF, the month and year (or year alone if month is not recorded) of onset determine whether an AE is treatment emergent.

The event is considered treatment emergent if both of the following 2 criteria are met:

- The month and year (or year) of the AE onset is **the same as or after** the month and year (or year) of the first dosing date of B/F/TAF, and
- The month and year (or year) of the AE onset is **the same as or before** the month and year (or year) of the date corresponding to 30 days after the date of the last dose of B/F/TAF

An AE with completely missing onset and stop dates or with the onset date missing and a stop date marked as ongoing or on or after the first dosing date of B/F/TAF, will be considered as a TEAE. In addition, an AE with the onset date missing and incomplete stop date with the same or later month and year (or year alone if month is not recorded) as the first dosing date of B/F/TAF will be considered as a TEAE.

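### An adverse event in four disease lists can count both as baseline history (SAP Appendix 5) and as treatment-emergent (SAP 7.1.5) when its date is the first-dose date, matches it only in part, or is missing

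*SAP*

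**What the plan says.** SAP 5.2 reports four medical-history items as Yes/No, and Appendix 5 defines them: "selected medical history of Diabetes Mellitus, Hypertension, Cardiovascular Disease, and Hyperlipidemia will be summarized by treatment as baseline disease characteristics". The answer is Yes if any one of three sources qualifies: a medical history record, an AE record or a concomitant medication record. The AE source reads "At least 1 adverse event record with MedDRA PT (ae.MDRPT) in the selected PT listing for the corresponding disease with start date"; that date may be no later than the day of first dose, which is itself included. Two date rules then apply to every source. A partial date counts under the rule that begins "If the start date is incomplete but the month and year (or year alone) of the start date is the same as or before the"; the comparison is with the first-dose period, at whatever precision was recorded. For an absent date, "If the start date is completely missing, the event will be included". The stop date plays no part in any of this.

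SAP 7.1.5.1, first bullet, defines treatment-emergent AEs as "Any AEs with an onset date on or after the B/F/TAF start date and no later than 30 days", with the upper limit counted from when study drug is stopped for good. Under 7.1.5.2, a partial onset in the same or a later month/year (or year) than first dose is treatment-emergent, up to the period containing last dose plus 30 days, unless the event stopped before first dose. "An AE with completely missing onset and stop dates or with the onset date missing and a stop date marked as ongoing" is also treatment-emergent, as is a missing onset with a stop on or after first dose.

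Protocol 7.2 limits what sites report as AEs between consent and first dose to "all SAEs and adverse events related to protocol-mandated procedures". Protocol 6.2.1 sends every other screening-period occurrence to the medical history form, which Appendix 5 already searches separately.

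**The concern.** Appendix 5 includes the first-dose date from one side and 7.1.5.1 includes it from the other. Both sections also admit onsets in the first-dose month/year and missing onsets. No text says that one class excludes the other, or which prevails. One record can therefore be reported as disease present before treatment and as an event arising on treatment.

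The first-dose date is the clearest case. Under the collection rules, an AE dated that day that is neither serious nor related to a study procedure should have begun after dosing, yet it sets a baseline flag. The cardiovascular lists make the conflict easy to see: SAP 7.1.7.2 states that the cardiovascular event table and the cardiovascular history search use the same preferred terms. Any cardiovascular AE with an overlapping date therefore enters both.

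At stake is how a single-arm study in people aged 65 or over is read. There is no comparator, so the baseline comorbidity row is part of the context for judging cardiovascular and metabolic events.

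**Working it through.** The plan states no figure to reproduce. The check is to apply both sets of rules to the same records.

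**Inputs.** History rule: SAP Appendix 5. Treatment-emergent onset rules: SAP 7.1.5.1 (first bullet) and 7.1.5.2. Ten start-date patterns were crossed with four stop-date patterns (ongoing, missing, before first dose, after first dose), using illustrative first- and last-dose dates. Of the 10 × 4 = 40 combinations, 5 are infeasible because the stop would precede the start, which leaves 35.

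| AE start date | Baseline history? | Treatment-emergent? | Both |
|---|---|---|---|
| Complete, day before first dose | yes | no | 0 of 3 |
| Complete, first-dose date | yes | yes | 3 of 3 |
| Complete, day after first dose | no | yes | 0 of 3 |
| Partial, earlier month/year or year | yes | no | 0 of 8 |
| Partial, same month/year or year | yes | yes, unless stopped before first dose | 6 of 8 |
| Partial, later month/year or year | no | yes | 0 of 6 |
| Missing | yes | yes, unless stopped before first dose | 3 of 4 |

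Overlap: 3 + 6 + 3 = 12 of 35. These are rule combinations, not subjects or records, and 12/35 is not a rate of anything in the data. If an AE record counts as history only when its onset does not make it treatment-emergent, the overlap is 0 of 35.

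**Size per subject.** The disposition mock-up in SAP Appendix 7 gives 86 subjects in the Safety Analysis Set. SAP 5.1 uses that set for baseline characteristics. SAP 5.2 names no set, so I assume the same one. The flag is set once per subject, so an overlapping record changes it only if nothing else qualifies that subject for the same disease. The most it can add is 1/86 = 0.0116, or 1.2 percentage points. The rule cannot lower the percentage.

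**The case against.** The strongest reply has four parts.

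- **Ambiguous dates.** With a partial or missing onset nobody knows whether the event preceded dosing. Calling it treatment-emergent is a conservative convention, not evidence that it is new.
- **Legitimate use.** A serious event during screening belongs on the AE form, not the history form, so Appendix 5 has reason to search AE records. How much of this source's contribution is overlap cannot be quantified.
- **Data quality.** A myocardial infarction or stroke would normally be serious. Such events are sent within 24 hours (Protocol 7.2.2) and reconciled before data finalization (SAP 7.1.4), so one with only a month of onset at final analysis is unlikely.
- **No downstream use.** There are no strata or covariates (SAP 3.3) and no subgroups (SAP 3.4, 7.7). The cardiovascular event table is by preferred term, not by baseline disease.

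All of this stands as a limit on the consequence. None of it reconciles the two rules, and the first-dose-date overlap does not depend on ambiguous dates at all.

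A reader might infer that every AE with a partial or missing start is counted twice. The table shows otherwise, and only terms in the four lists are involved. A reader might also infer that new on-drug events are being presented as prior disease. For partial or missing dates that is not established; what is established is that one record receives two incompatible labels.

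**Conclusion.** The contradiction is in the text, and the consequence is small. It covers AE records in the diabetes, hypertension, cardiovascular and hyperlipidemia lists that meet one of three conditions:

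- onset on the first-dose date;
- a partial onset matching the first-dose month/year (or year), with a stop not before first dose;
- a missing onset, with a stop that is missing, ongoing, or on or after first dose.

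The effect is upward only and confined to the descriptive history row. The 1.2 points is a ceiling per affected subject. It is tempting to apply it to each overlapping record, but a second record, or a subject already flagged from another source, adds nothing. The documents give no count of affected records, and it may be zero. Treatment-emergent counts and the virologic endpoints are untouched. It is worth correcting because a stated rule yields an inconsistent baseline flag and the remedy is almost free.

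**What to change.** In Appendix 5, do not use an AE record as baseline history if its onset makes it treatment-emergent under 7.1.5.1 (first bullet) or 7.1.5.2. Refer to the first bullet only: the second takes any AE leading to discontinuation whatever its onset, and an event that truly began before dosing should stay in history.

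Keep AE records with an earlier complete date or an earlier month/year, and those with a partial or missing start that stopped before first dose. Requiring the start itself to be shown earlier than first dose would wrongly drop that last group.

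Leave the medical history source unchanged. The medication source follows the same date rules, and its cardiovascular list includes myocardial infarction and stroke as indications. Check that a drug given for the same on-treatment event does not restore the flag.

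The cost is one condition in the derivation program and a short review of medication records. A serious event that began before dosing on the first-dose day would then count only as treatment-emergent, as 7.1.5.1 already classes it. If the SAP is final, record the change and the number of overlapping records in the clinical study report, where SAP Section 1 places later changes.
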